#### 6. Short Form 36 (SF-36, version 2, acute)

The SF-36v2 (Acute) is a 36-item generic health status measure. It measures 8 general health domains: physical functioning, role limitations due to physical health, bodily pain, general health perceptions, vitality, social functioning, role limitations due to emotional problems, and mental health. These domains can also be summarized as physical and mental component summary scores.

These 8 domains are as follows:

- a. Physical Functioning (PF). This score is based on the responses to the 10 items that compose Question 3 and reflects the degree to which various physical activities have been limited in the previous week by the subject's health.
- b. Role-Physical (RP). This score is based on the responses to the four items that compose Question 4 and reflects the relative amount of time that the subject has had problems with work or other regular daily activities as a result of their physical health during the previous week.
- c. Bodily Pain (BP). This score is based on the responses to Questions 7 and 8 and reflects bodily pain and its effects on normal work during the previous week.
- d. General Health (GH). This score is based on responses to Question 1 and the four items in Question 11 and reflects the subject's perception of their general health during the previous week.
- e. Vitality (VT). This score is based on responses to Question 9 items a, e and g, and reflects the subject's physical energy level relative to time during the previous week.
- f. Social Functioning (SF). This score is based on responses to Questions 6 and reflects how physical health or emotional problems have interfered with social activities during the previous week.

- g. Role-Emotional (RE). This score is based on responses to the three items in Question 5 and reflects the amount of time during the previous week that emotional problems have interfered with work or regular daily activities.
- h. Mental Health (MH). This score is based on responses to Question 9 items b, c, d, f, and h and reflects various mental/emotional states relative to time during the previous week.

The summary component scores are:

- Physical Component Summary (PCS).
- Mental Component Summary (MCS).

In addition, there is another subscale in the SF-36: Health Transition (TR). This score is based on the response to Question 2 and is a rating of current general health compared to one week previous.

The summary component scores, PCS and MCS, are based on a normalized sum of the 8 scale scores PF, RP, BP, GH, VT, SF, RE, and MH. All domains and summary components are scored such that a higher score indicates a higher functioning or health level.

ILL DI L DI D	DEDUCTION
VARIABLE	DERIVATION
SF-36 PF scale score	raw score = sum (items 3A, 3B, 3C, 3D, 3E, 3F, 3G, 3H, 3I, 3J)
	PF = (raw score -10) * 5
	$PF_Z = (PF - 82.62455) / 24.43176$
	$PF scale score = (PF_Z*10) + 50$
	When calculating the raw score, if 5 or more of the items are non-missing then replace any missing values as follows:
	Calculate the mean of the answered questions, using the number of answered questions as the denominator. Substitute the mean for any missing scores. Otherwise, if less than 5 of the items are non-missing then PF scale score is missing.
	The response scale for each activity ranges from 1 to 3 where 1=limited a lot, 2=limited a little, and 3=not limited at all.
	A higher PF scale score indicates better physical functioning.

#### Data Derivation Details to Obtain Scale Scores for SF-36

SF-36 RP scale score	$ \begin{array}{l} \mbox{raw score} = \mbox{sum (items 4A, 4B, 4C, and 4D)} \\ \mbox{RP} = \ \ \ \ \ \ \ \ \ \ \ \ \ \ \ \ \ \ $
	When calculating the raw score, if 2 or more of the items are non-missing then replace any missing values as follows:
	Calculate the mean of the answered questions, using the number of answered questions as the denominator. Substitute the mean for any missing scores. Otherwise, if less than 2 of the items are non-missing then RP scale score is missing.
	The response scale for each item ranges from 1 to 5 where 1=All of the time, 2=Most of the time, 3=Some of the time, 4=A little of the time, and 5=None of the time.
	A higher RP scale score indicates better role-physical functioning.

SF-36 BP scale score	row googo - sum (rowarsod itom 7 and rowarsod itom 0)
SF-30 BP scale score	raw score = sum (reversed item 7 and reversed item 8) BP = (raw score -2) * 10
	BP Z = (BP - 73.86999) / 24.00884
	$BP \text{ scale score} = (BP_Z * 10) + 50$
	$\mathbf{D} = \mathbf{S} \mathbf{C} \mathbf{D} \mathbf{C} = (\mathbf{D} \mathbf{D} \mathbf{D} \mathbf{D} \mathbf{D} \mathbf{D} \mathbf{D} \mathbf{D} $
	Reverse direction of Item 7 as follows :
	if = 1, set to 6 if = 2, set to 5.4
	if =2, set to 5.4 if =3, set to 4.2
	if = 4, set to 3.1
	if = 5, set to 2.2
	if = 6, set to 1
	Reverse direction of item 8 as follows: if =1 and original value of item 7=1, set to 6
	if =1 and original value of item 7>=2, set to 5 if =2, set to 4
	if = 3, set to 3
	if = 4, set to 2
	if = 5, set to 1
	1 5,5000
	If item 7 is answered and item 8 is missing, set $8 =$ reversed 7 as defined above.
	If 8 is answered and 7 is missing, set 7 as reverse item 8 as follows:
	if $=1$ , set to 6
	if = 2, set to 4.75
	if=3, set to 3.5
	if=4, set to 2.25
	if=5, set to 1
	If 1 or more questions were answered, calculate BP scale score as defined above.
	If neither question was answered then BP scale score is missing.
	The scale for Question 7, amount of bodily pain, ranges from 1 to 6
	where 1=None, 2=Very mild, 3=mild, 4=Moderate, 5=Severe, and
	6=Very severe.
	The scale for Question 8, the degree to which pain interfered with normal work,
	ranges from 1 to 5 where 1=Not at all, 2=A little bit, 3=Moderately, 4=Quite a bit,
	and 5=Extremely.
	A higher BP scale score indicates lack of bodily pain.

SF-36 GH scale score	raw score = sum (reversed item 1, item 11A, reversed 11B,
	11C and reversed 11D)
	GH = (raw score - 5) * 5
	GH Z = (GH - 70.78372) / 21.28902
	$\overline{GH}$ scale score = ( $\overline{GH}$ $Z$ * 10) + 50
	Reverse direction of Item 1 as follows:
	if = 1, set to 5
	if = 2, set to 4.4
	if = 3, set to 3.4
	if =4, set to 2
	if =5, set to 1
	Reverse direction of item 11B and 11D by subtracting score from 6.
	When calculating the raw score, if 3 or more of the items are non-missing then
	replace any missing values as follows:
	Calculate the mean of the answered questions, using the number of answered
	questions as the denominator. Substitute the mean for any missing scores.
	Otherwise, if less than 3 of the items are non-missing then GH scale score is
	missing.
	Responses for Question 1, an assessment of self-perceived health status, range
	from 1 to 5 where 1=Excellent, 2=Very good, 3=Good, 4=Fair, and 5=Poor.
	Responses for the items in Question 11 range from 1 to 5 where 1=Definitely true,
	2=Mostly true, 3=Don't know, 4=Mostly false, and 5=Definitely false and reflect
	the subject's perception of their relative health and expectations of their future
	health status.
	A higher GH scale score indicates better general health perceptions.
	ringher off some soore indicates soure general neural perceptions.

SF-36 VT scale score	raw score = sum (reversed item 9a, reversed 9e, 9g and 9i) $VT = \int_{-\infty}^{\infty} \frac{4}{161} \frac{1}{160} \frac{1}{160$
	VT = [(raw score -4)/16] * 100 VT Z = (VT - 58.41968) / 20.87823
	$V_{1_2} = (V_{1_2} - 36.41968) / 20.67825$ VT scale score = (VT Z * 10) + 50
	(1  scale scole - ((1  1  2  10) + 50)
	Reverse direction of Items 9a and 9e by subtracting score from 6.
	When calculating the raw score, if 2 or more of the items are non-missing then replace any missing values as follows:
	Calculate the mean of the answered questions, using the number of answered questions as the denominator. Substitute the mean for any missing scores.
	Otherwise, if less than 2 of the items are non-missing then VT scale score is missing.
	The scale for these items ranges from 1 to 5 where 1=All of the time, 2=Most of the time, 3=Some of the time, 4=A little of the time, and 5=None of the time.
	A higher VT scale score indicates more vitality.
SF-36 SF scale score	raw score = sum (reversed 6 and 10)
	SF = [(raw score -2) / 8] * 100
	$SF_Z = (SF - 85.11568) / 23.24464$
	SF scale score = $(SF_Z * 10) + 50$
	Reverse direction of score for item 6 by subtracting score from 6.
	When calculating the raw score, if 1 of the items is missing then substitute the missing score with the score on the non-missing item. If both items are missing then SF scale score is missing.
	Responses to Question 6, an assessment of the extent to which health/emotional problems interfered with social activities, range from 1 to 5 where 1=Not at all, 2=Slightly, 3=Moderately, 4=Quite a bit, and 5=Extremely.
	Responses to Question 10 reflect the amount of time that health/emotional problems interfered with social activities and range from 1 to 5 where 1=All of the time, 2=Most of the time, 3=Some of the time, 4=A little of the time, and 5=None of the time.
	A higher SF scale score indicates better social functioning.

SF-36 RE scale score	raw score = sum (items 5A, 5B, and 5C)
	RE = [(raw score -3) / 12] * 100
	$RE_Z = (RE - 87.50009) / 22.01216$
	RE scale score = $(RE_Z * 10) + 50$
	When calculating the raw score, if 2 or more of the items are non-missing then replace any missing values as follows:
	Calculate the mean of the answered questions, using the number of answered questions as the denominator. Substitute the mean for any missing scores. Otherwise, if less than 2 of the items are non-missing then RE scale score is missing.
	Responses to the items in Question 5 range from 1 to 5 where 1=All of the time, 2=Most of the time, 3=Some of the time, 4=A little of the time, and 5=None of the time.
	A higher RE scale score indicates better role-emotional functioning.
SF-36 MH scale score	raw score = sum (items 9B, 9C, reversed 9D, 9F and reversed 9H) MH = (raw score - 5) * 5 MH_Z = (MH - 75.76034) / 18.04746
	MH scale score = $(MH_Z * 10) + 50$
	Reverse direction of scores for 9D and 9H, by subtracting score from 6.
	If 3 or more of the items are non-missing then replace any missing values as follows:
	Calculate the mean of the answered questions, using the number of answered questions as the denominator. Substitute the mean for any missing scores. Otherwise, if less than 3 of the items are non-missing then MH scale score is missing.
	The scale for these items ranges from 1 to 5 where 1=All of the time, 2=Most of the time, 3=Some of the time, 4=A little of the time, and 5=None of the time.
	A higher MH scale score indicates better mental health.
SF-36 TR scale score	raw score = item 2 TR scale score = raw score
	The scale for this item ranges from 1 to 5 where 1=Much better now than one week ago, 2=Somewhat better now than one week ago, 3=About the same as one week ago, 4=Somewhat worse now than one week ago, and 5=Much worse now than one week ago.
	A higher TR scale score indicates worse general health currently relative to one week previous.

SF-36 PCS score	PCS score includes the 8 scales for GH, PF, RP, RE, SF, MH, BP, and VT.
	PF1= (PF-82.62455)/24.43176;
	RP1=(RP-82.65109)/26.19282;
	BP1=(BP-73.86999)/24.00884;
	GH1 = (GH-70.78372)/21.28902;
	VT1= (VT-58.41968)/20.87823;
	SF1=(SF-85.11568)/23.24464;
	RE1= (RE-87.50009)/22.01216;
	MH1=(MH-75.76034)/18.04746;
	Raw Score = ((GH1*.24954)+(PF1*.42402)+(RP1*.35119)
	+ (RE1*19206)+(SF1*00753)+(MH1*22069)+(BP1*.31754)
	+ (VT1*.02877))
	PCS Summary Scale Score = (raw score *10) + 50
	Raw Score is missing if one of the component scale scores is missing.
SF-36 MCS score	MCS score includes the 8 scales for GH, PF, RP, RE, SF, MH, BP, and VT.
	PF1= (PF-82.62455)/24.43176;
	RP1=(RP-82.65109)/26.19282;
	BP1=(BP-73.86999)/24.00884;
	GH1 = (GH-70.78372)/21.28902;
	VT1 = (VT-58.41968)/20.87823;
	SF1=(SF-85.11568)/23.24464;
	RE1= (RE-87.50009)/22.01216;
	MH1=(MH-75.76034)/18.04746;
	Raw Score =((GH1*01571)+(PF1*22999)+(RP1*12329)
	$+ (RE1^*.43407) + (SF1^*.26876) + (MH1^*.48581) + (BP1^*-0.09731)$
	$+(VT1^*.23534))$
	MCS Summary Scale Score = (raw score*10)+50
	Raw score is missing if one of the component scale scores is missing.

# 7. EuroQol-5D Health Questionnaire – 3 Level (EQ-5D-3L)

On the EQ-5D (subject version, 3 categories of response per question), 5 dimensions of health (mobility, self-care, usual activities, pain/discomfort and anxiety/depression) are assessed. The status of each dimension has three possible responses (no problem in the relevant health dimension to severe problems). The EQ-VAS records the patient's self-rated health on a vertical visual analogue scale where the endpoint is labelled 'Best imaginable health state' and 'Worst imaginable health state'. Based on the patient's mark on the VAS form a score ranging from 0 to 100 mm is recorded.

# 8. DAS28-3(CRP)

PFIZER CONFIDENTIAL Page 54

The Disease Activity Score (DAS) is a derived measurement with differential weighting given to each component. DAS28-3(CRP) will be calculated from measurements made at all study visits (Madsen et al., 2011).

The components of the DAS28-3 arthritis assessment are:

- 1) Tender/Painful Joint Count (28);
- 2) Swollen Joint Count (28);
- 3) C-Reactive Protein (CRP in mg/L).

DAS28-3(CRP) = [0.56\*sqrt(TJC28) + 0.28\*sqrt(SJC28) + 0.36\*ln(CRP+1)]\*1.10 + 1.15

where sqrt() refers to the square root, and ln() refers to the natural logarithm.

The swollen joint count (28) and tender/painful joint count (28) will be calculated similarly as for the swollen joint count (66) and tender/painful joint count (68) per Section 9 and Section 10 in Appendix 3.

Any missing component will result in DAS28-3(CRP) as missing. A higher score represents a more severe disease activity.

## 9. Swollen Joint Count (66)

Swollen joints are recorded in the CRF page of joint swelling. For each of the 66 joints, swelling can be recorded as "Present", "Absent", "Not Done", "Not Applicable" or this joint assessment is simply missing. Before calculating the swollen joint count, the following pre-processing steps for each joint should be performed per Pfizer's standard:

- If a joint receives an intra-articular injection (either at Baseline or post-baseline visits), set the joint status to "Present" on or after the date of injection regardless of the assessment of the joint recorded on the CRF page.
- If there is no associated injection record available, a joint recorded as "Not Done" is set to missing.
- A joint recorded as "Not Applicable" means that measurement cannot be made and this joint is set to missing.

After this pre-processing, a joint assessment that is set to missing is to be imputed by the average of the non-missing values of the other joints, with the restriction that the number of missing joint assessments cannot exceed 50% of the expected total number of joints evaluated for the swollen joint count (i.e., 33, 50% of 66). In that case, the swollen joint count is set to missing.

Explicitly after pre-processing, let

- N1=number of joints recorded as "Present";
- N2=number of joints recorded as "Absent";
- N3=number of joints with missing values.

The total number of joints assessed is  $N_1 + N_2 + N_3$  (i.e., 66). The calculated swollen joint count is therefore  $N_1 + N_3 \times (N_1/(N_1 + N_2))$  if  $N_1 + N_2 > 33$ ; otherwise the swollen joint count is set to missing. The calculated swollen joint count will be rounded to a whole number. For example, a value of 24.5 is rounded to 25, a value of 24.49 is rounded to 24. Note that if there is no missing joint assessment, the swollen joint count will be the number of joints recorded as "Present" (i.e.,  $N_1$ ).

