Currently 5 tumour necrosis factor inhibitors (TNFi) are approved by the US FDA for use in PsA: infliximab, etanercept, adalimumab, golimumab, and certolizumab. Within the last few years, additional biologic disease-modifying anti-rheumatic drugs (bDMARDs) have been approved for PsA including ustekinumab (a human mAb interleukin-12 and IL-23 antagonist) and secukinumab (a human mAb interleukin-17A antagonist). These bDMARD therapies have demonstrated statistical significance versus placebo on ACR 20/50/70 responses; as well as efficacy in other PsA domains.

TNFi and Apremilast are not approved in China for the treatment of PsA. There is therefore unmet medical need for new disease-modifying anti-rheumatic drugs (DMARDs) in the PsA patient population in China where there is no approved biologic/TNFi for PsA and treatment alternatives are insufficient.

This trial will use placebo control in the study design to provide rigorous hypothesis testing and unequivocal scientific data to evaluate the efficacy and safety profile of tofacitinib in Chinese PsA patient population. The placebo control period will be 3 months in duration which should be adequate time to see effects of active treatment on signs/symptoms of PsA and minimize the amount of structural damage incurred. Subjects who enroll in this study should remain on their concomitant non-biologic DMARDs as noted in the inclusion/exclusion criteria. In addition, subjects may be offered an appropriate rescue medication (see Appendix 5) during the study if there is an increase in pain. Finally, if subjects do experience an increased or persistent clinical disease activity, they will have the option to withdraw from the study at any time.

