# 5.9. Rescue Therapy

The only medications that are allowed for rescue are listed in Appendix 5.

Increases of acetaminophen/paracetamol and opioids are allowable as rescue medication for no more than 10 consecutive days. Acetaminophen/paracetamol may be added or increased to a maximum of 2.6 gm/day. Opioids may be added or increased to a maximum potency equivalent of 30 mg of orally-administered morphine. Acetaminophen/paracetamol is not permitted as a part of combination products such as over-the-counter "cold remedies" or in combination with opioids if the total acetaminophen/paracetamol dose will exceed 2.6 gm/day.

Subjects who require rescue for more than 10 consecutive days should be discontinued from the study. There is no limit to the duration of nonconsecutive use of rescue medications. In addition, subjects may not be dosed with rescue medication during the 24 hours prior to a study visit. Baseline stable use acetaminophen/paracetamol or opioids should NOT be discontinued in advance of study visits.

A maximum of 40 mg methylprednisolone or equivalent of intraarticular corticosteroids will be allowed as rescue medication at or after the Month 3 visit; intraarticular corticosteroid injections should not be performed within the 4 weeks prior to a study visit. The total allowed intraarticular corticosteroid dose may be divided into separate injections (eg, 20 mg, 20 mg). Intra-articular hyaluronate sodium injections may be administered for indications in accordance with the local label at or after the Month 3 visit in no more than two joints. If performed at Month 3 visit, intra-articular injections must be given after the assessments are completed.

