#### 7.2.3. Swollen Joint Count (66)

The blinded assessor will also assess joints for swelling using the following scale: Present/Absent/Not Done/Not Applicable (to be used for artificial or missing joints).

Sixty-six (66) joints will be assessed for swelling, the same as those listed above for tenderness/pain, except that the right and left hip joints are not included in the swollen joint count. Artificial joints will not be assessed.

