#### For subjects who ARE on stable, background opioid therapy:

- They may NOT add a second opioid agent for rescue;
- If their background medication is 1 of the 3 listed above, they may, within the above maximum total dosage limits, increase the dosage for up to 10 consecutive days for rescue purposes;
- If their background medication is a short-acting (half-life <5 hrs, Appendix 4) opioid that is not one of those listed above, they may increase the dosage for up to 10 consecutive days (up to a total daily dose which must not exceed the potency equivalent of 30 mg of orally-administered morphine [Appendix 4]) for rescue purposes;
- Sustained release opioid formulations (eg, OxyContin®, MS Contin®) and opioids with half lives greater than 5 hours (eg, methadone, propoxyphene) may NOT be USED for rescue medication.

Sustained release opioid formulations (eg, OxyContin®, MS Contin®) and opioids with half lives greater than 5 hours (eg, methadone, propoxyphene; see also Appendix 4) may NOT be INCREASED for rescue purposes.

Intravenous or intramuscular corticosteroids, biologic response modifiers and DMARDs, other than methotrexate and sulfasalazine, are not allowed during this study. Intra-articular corticosteroids may be given at or after the Month 3 visit in no more than two joints, in a cumulative dose of no more than 40 mg methylprednisolone or its equivalent in any 6 month study period. The total allowed intraarticular corticosteroid dose may be divided into separate injections (eg, 20 mg, 20 mg). Intra-articular hyaluronate sodium injections may be administered for indications in accordance with the local label at or after the Month 3 visit, intra-articular injections must be given after assessments are completed. Intra-articular corticosteroids should not be administered within 4 weeks prior to a study visit.

Acetaminophen/paracetamol is not permitted as a part of combination products such as over-the-counter "cold remedies" or in combination with opioids if the acetaminophen/paracetamol dose will exceed 2.6 gm/day. Subjects who require rescue for more than 10 consecutive days should be discontinued from the trial. In addition, subjects should not be dosed with rescue acetaminophen/paracetamol or opioids within 24 hours prior to a study visit. Baseline stable acetaminophen/paracetamol or opioids should NOT be discontinued in advance of study visits.

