#### 5.3. Methods to Manage Missing Data

As stated in the protocol, in the primary analysis of the primary endpoint, ACR50 response rate at Month 3, missing values for any reason, e.g., due to a subject dropping from the study or due to the impact of COVID-19 pandemic, will be handled by setting the ACR50 value to nonresponsive. Note that this can be viewed as a composite endpoint in the sense that a response requires the subject completes a visit of interest, e.g., Month 3, and achieves a response per the defined ACR50 response criteria (otherwise it is considered a nonresponse). This method of handling missing response is known as missing response as non-response (MR=NR). This MR=NR approach will be used for all "response-type" endpoints at all timepoints except for the supportive analyses using GMMRM (see Section 5.2.1.2) and Tipping Point Analysis (see Section 5.2.1.3) for ACR50 up to Month 3. Note that if a subject

discontinues from the study at a visit of interest, say Month 3, but the value of the endpoint is not missing at Month 3, the value of the endpoint will be used for Month 3.

For a composite "response-type" endpoints (such as ACR50), if values in any of the components at a timepoint are missing, the component variables that are not missing will be used to determine the response status. If one could not determine the response status in the presence of missing components at the timepoint, then the composite response-type endpoint status is considered as missing and is handled by MR=NR for that timepoint for all of the inferential analyses except for the supportive analyses using GMMRM (see Section 5.2.1.2) and Tipping Point Analysis (see Section 5.2.1.3) for ACR50 up to Month 3.

Repeated measures data for continuous and ordered-categorical (analyzed as continuous) endpoints will be analyzed with MMRM. This model will yield unbiased estimates and valid inferences in the presence of data that is MCAR or missing at random (MAR). Given that subjects who drop out are scheduled to have an end of study evaluation, the more stringent condition of MAR (Rubin, 1987) is believed to be a reasonable assumption. Hence missing values will not be imputed in the routine analysis using the repeated measures model.

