## Appendix 2. DEFINITION AND USE OF VISIT WINDOWS IN REPORTING

For reporting purposes, the following visit windows will be used for efficacy/PRO variables and for any safety displays that display by week/month. All observations regardless of on- or off-treatment will be used. For an endpoint that consists of multiple components, e.g., ACR50 and DAS28-3(CRP), the components should be collapsed first in the same visit window to derive the endpoint.

If two or more visits/observations fall into the same window, the visit/observation closest to the target day will be used in the analyses. If there is a tie, the later visit/observation will be used. However, for a subject who discontinues from the study early prior to the Month 6 visit and who does not have an observation within the Month 6 visit window, if two or more observations fall in the same visit window (i.e., a visit window prior to Month 6), then the latest observation (rather than the observation closest to the target day) within this visit window will be used in the analysis for that visit window.

Visit Label	Target Day	Definition [Day Window]
Screening		< Day 1
Baseline	Day 1	Last non-missing assessment on or before Day 1 and prior to first dose of study drug administration
Week 2	Day 15	Day 2 to Day 21
Month 1	Day 29	Day 22 to Day 42
Month 2	Day 57	Day 43 to Day 70
Month 3	Day 85	Day 71 to [Treatment Switch Day or Day 98, whichever is smaller]
Month 4	Day 113	[Treatment Switch Day + 1 or Day 99, whichever is smaller] to Day 140
Month 6	Day 169	≥ Day 141

Target day is equal to the target week  $\times$  7 days + 1 day. A month is 4 weeks or 28 days.

Treatment Switch Day = date of the first dose of treatment switch at month 3 (i.e., treatment switch date – date of the first dose + 1). The first dose of the treatment switch at Month 3 will be taken from the first dosing date from the Month 4 oral dosing CRF.

All the data collected on the treatment switch day will be counted in  $\leq$  Month 3 except for the AE data. Any new treatment emergent AE occurred on the day of treatment switch will be counted in  $\geq$  Month 4.

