## 10. Tender/Painful Joint Count (68)

Tender/painful joints are recorded in the CRF page of joint tender/painful. For each of the 68 joints, tender/painful can be recorded as "Present", "Absent", "Not Done", "Not Applicable" or this joint assessment is simply missing. The tender/painful joint count will be calculated per Pfizer's standard similarly as for the swollen joint count (see Appendix 3 Section 9).

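### The SAP resets an injected joint to Present from the injection date itself, so an injection given after the Month 3 assessment overwrites that day's Absent reading in the primary ACR50 (minor, cheap to fix)

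*SAP*

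**What the plan says.** **Derivation.** SAP Appendix 3, Section 9 pre-processes each joint before counting. A joint that receives an intra-articular injection is set to Present "on or after the date of injection regardless of the assessment of the joint recorded on the CRF page". The rule is described as the sponsor's standard. Section 10 carries it over: "The tender/painful joint count will be calculated per Pfizer's standard similarly as for the swollen joint count".

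**Order of events at the visit.** Protocol 5.9 first allows intra-articular corticosteroid and hyaluronate at the Month 3 visit and states: "If performed at Month 3 visit, intra-articular injections must be given after the assessments are completed". Protocol 7.2.3 assigns the reading to a blinded rater: "The blinded assessor will also assess joints for swelling using the following scale".

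**Number of joints.** For corticosteroid, Protocol Appendix 5 says: "Intra-articular corticosteroids may be given at or after the Month 3 visit in no more than two joints". Protocol 5.9 sets a separate limit of two joints for hyaluronate. No combined limit is stated.

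**Route to the primary endpoint.** SAP Appendix 2 says "All the data collected on the treatment switch day will be counted in" the period up to Month 3, adverse events apart. ACR50 requires at least 50% improvement in both joint counts (Protocol 7.1.1; SAP Appendix 3, Section 1). The primary analysis uses the full analysis set (SAP 6.1.1.1).

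**The concern.** An injection given after the assessment cannot have influenced the reading. The rule makes sense for later assessments, where the injection itself may have suppressed swelling or tenderness. Because it includes the injection date, it also discards a blinded reading made before any rescue, and the SAP gives no reason for doing so. A subject who met ACR50 at Month 3 on the recorded data could be counted as a non-responder in the primary analysis because of something done later that day.

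The missing-data rule does not account for this. Non-responder imputation in SAP 5.3 applies to missing responses, and neither document makes rescue a non-response. For a subject who discontinues at the Month 3 visit "but the value of the endpoint is not missing at Month 3, the value of the endpoint will be used for Month 3", so observed values are otherwise kept.

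**Working it through.** **1. Does the overwrite reach the primary endpoint?** For a subject injected on the Month 3 visit day in the protocol's order:
- The joint is read, then injected (Protocol 5.9).
- The injection date equals the assessment date, so Section 9 applies and Absent becomes Present.
- That day's data belong to Month 3 (SAP Appendix 2).
- Both counts are mandatory for ACR50, so the changed count decides response.

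Neither document exempts a same-day reading made before the injection.

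**2. When does the overwrite change response?** Let B be the baseline count, c the recorded Month 3 count and m the number of Absent joints reset to Present, with no missing joints. The largest qualifying count is floor(B/2). A subject who otherwise meets ACR50 is lost when c ≤ floor(B/2) < c + m. Improvement is 1 − count/B.

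| B | c | m | Count becomes | Improvement |
|---|---|---|---|---|
| 3 | 1 | 1 | 2 | 67% to 33% |
| 4 | 2 | 1 | 3 | 50% to 25% |
| 5 | 2 | 1 | 3 | 60% to 40% |
| 6 | 3 | 1 | 4 | 50% to 33% |
| 5 | 1 | 2 | 3 | 80% to 40% |

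Low baselines occur by design: entry needs only 3 swollen joints (Protocol 4.1.1), and up to about 78 subjects may have a baseline swollen count of 5 or fewer (Protocol 3). Because the two-joint limits are separate, m is not strictly capped at 2.

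**3. The plan's own figure.** Inputs from Protocol 9.1: 136 and 68 subjects, 9.5% on placebo, a difference of 18.5 points (so 28.0% on tofacitinib), two-sided 5%, at least 90% power. With the unpooled standard error of SAP 5.2.1.1:
- SE = √(0.28×0.72/136 + 0.095×0.905/68) = 0.0524.
- 0.185/0.0524 = 3.53, and power = Φ(3.53 − 1.96) = 94.2%.
- Counting the 11 COVID-19 missing values as non-responders multiplies both rates by 193/204 (26.5% and 9.0%) and gives 92.6%.

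The stated power is reproduced with this statistic.

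**4. Weight of one changed subject.** A lost tofacitinib responder moves the difference by −1/136 = −0.7 points. A lost placebo responder moves it by +1/68 = +1.5 points.

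**5. Effect on significance.** Planning rates give 0.28×136 = 38.1 and 0.095×68 = 6.5 responders, so 38 against 6 and 38 against 7 are both used. The documents give no count of affected subjects; 1 to 3 is an assumption for illustration. Example for 38 against 6: Z = (0.2794 − 0.0882)/√(0.2794×0.7206/136 + 0.0882×0.9118/68) = 0.1912/0.0516 = 3.70, p = 0.0002.

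| Tofacitinib responders lost | p, placebo 6/68 | p, placebo 7/68 |
|---|---|---|
| 0 | 0.0002 | 0.0009 |
| 1 | 0.0003 | 0.0014 |
| 2 | 0.0006 | 0.0022 |
| 3 | 0.0009 | 0.0033 |

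Significance is first lost at 24 against 6 (p = 0.063; 38 − 24 = 14 lost) or 27 against 7 (p = 0.057; 38 − 27 = 11 lost). A single change crosses 0.05 only in a borderline trial, for example 25 against 6 (p = 0.046) becoming 24 against 6 (p = 0.063).

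**6. Effect on power.** If every loss fell on tofacitinib, power would be 92.6%, 90.6% and 88.3% for 1, 2 and 3 losses (90.7%, 88.4% and 85.7% with the 11 missing as non-responders). This is a one-sided worst case; placebo losses would widen the difference.

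**The case against.** **It is a disclosed convention.** The rule is stated openly. The protocol passage governs what sites do and the SAP passage governs derivation, so both can be followed. This stands: a reader might infer that the SAP contradicts the protocol, and it does not. It remains true that no reason is given for letting a later event replace a blinded reading.

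**Only dates are recorded.** Protocol 5.8 asks for start and stop dates of medication and mentions no time of day, so a date-inclusive rule looks prudent. At Month 3, however, the protocol itself fixes the order, and a breach of it would be a deviation.

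**The case is rare.** It needs a rescue injection on the visit day, in a joint read as Absent on at least one count, in a subject who otherwise meets ACR50 and lies close to the limit. Protocol 1.2 says "subjects may be offered an appropriate rescue medication (see Appendix 5) during the study if there is an increase in pain", which seldom goes with such a response. Protocol 5.9 also says that corticosteroid injections should not fall within 4 weeks before a visit. Month 3 (Day 85) and Month 4 (Day 113) are exactly 28 days apart, which leaves no room for an early Visit 6, although hyaluronate is not restricted in this way. All of this stands and is why the point is small. A joint injected for pain can still be recorded as not swollen, so the case is not empty.

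**A check is already planned.** The per-protocol set drops subjects with rescue on the day of the Month 3 assessment or the day before (SAP 4.2.2; Supportive Analysis 1 in SAP 6.1.1.2). That analysis does not depend on the overwritten values, but it does not restore them in the primary analysis.

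**Conclusion.** The point holds as a minor one. On the text, a valid Absent reading made before a same-day Month 3 injection is overwritten in the primary analysis, and for an affected subject the change can only remove a response. The documents give no injection frequency; that few subjects are affected is a judgement from the restrictions on rescue.

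Two stronger readings are not supported:
- A reader might infer a bias against tofacitinib. The documents give no injection frequency by arm, and each placebo responder lost moves the difference twice as far, in the opposite direction.
- A reader might infer a threat to the primary conclusion. At the planning rates 1 to 3 changed subjects leave significance intact; 11 to 14 would be needed, all on tofacitinib.

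The arithmetic assumes the planned arm sizes and rates, complete joint assessments (Section 9 extrapolates for missing joints) and injections given in the protocol's order. The rule is not disputed for assessments made after an injection.

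**What to change.** Add to SAP Appendix 3, Section 9, and carry into Section 10:

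*For an intra-articular injection on the date of the joint assessment at the scheduled Month 3 visit (Visit 5), the recorded joint status is used at Month 3, unless a protocol deviation recorded before unblinding shows that the injection preceded the assessment. The joint is set to Present for all assessments after that date.*

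Leave the rule unchanged for all other visits and for a joint recorded as Not Done that has an injection record. No dose or rescue rule changes.

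The cost is one sentence and one date condition in the program; injection times are not needed. The downsides are that the exception relies on the protocol-required order and on sites reporting departures from it, and that it moves slightly away from the sponsor's standard. Month 3 would also be derived differently from Months 4 and 6 in every endpoint that uses these counts. Protocol Appendix 5, as printed, may extend the assess-first order to later visits. Limiting the exception to Month 3 confines it to the visit where Protocol 5.9 is explicit and where the primary endpoint is measured.
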